## 7.3 First Follow-up Encounter (Encounter # 2)

At the completion of 4 weeks ( $\pm$  4 days) post-index date, the Site Investigator and Subjects will be asked to complete the first follow-up data collection, conducted via in-person or virtual/remote visits.

The patients will be advised to visit their site/clinician's offices to do the following:

- Drop off the first tablet/pill bottle of Seysara® (bottle # 1) supplied to them at study start, be it empty or with left-over pills.
  - This may be done as curb-side interaction, without entering clinician's offices.
- Pick-up the second bottle of Seysara® supply (bottle # 2) for the next four weeks of use.
  - This may be done as curb-side interaction, without entering clinician's offices.
- Undergo AV clinical evaluation inside clinician's office, if feasible.

The Site Investigators will complete the following, based on the information documented in patient medical charts and per clinical judgment guided by observing study subject via in-person or virtual/remote visit:

- IGA of current AV severity on the face.
- Patient treatment compliance, per sarecycline pill/tablets left over in the subject-returned bottle.

- Modifications to sarecycline treatment characteristics (e.g., change in dose, discontinuation), in the past 4 weeks, if any.
- AEs (incl. SAEs) related to or possibly related to sarecycline, observed in the past 4 weeks, as documented in the medical charts.
- Information on withdrawal from study (if occurred within the past 4 weeks).

The study Subjects will provide the following information via online survey portal or a mobile app: perceptions of current AV-related signs/severity. In case of pediatric patients, this information will be obtained from parents/caregivers as well.

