#### **7.4 Second Follow-up Encounter (Encounter # 3)**

At the completion of 8 weeks ( $\pm$  4 days) post-index date, the Site Investigators and Subjects will be asked to complete the second follow-up data collection, conducted via in-person or virtual/remote visits.

The patients will be advised to visit their site/clinician's offices to do the following:

- Drop off the second tablet/pill bottle of Seysara® (bottle # 2) supplied to them at the Wk-4 visit, be it empty or with left-over pills.
  - This may be done as curb-side interaction, without entering clinician's offices.
- Pick-up the third bottle of Seysara® supply (bottle # 3) for the next four weeks of use.
  - This may be done as curb-side interaction, without entering clinician's offices.
- Undergo AV clinical evaluation inside clinician's office, if feasible.

The Site Investigator will complete the following, based on the information documented in patient medical charts and per clinical judgment guided by observing study subject via in-person or virtual/remote visit:

- IGA of current AV severity on the face.

- Patient treatment compliance, per sarecycline pill/tablets left over in the subject-returned bottle.
- Modifications to sarecycline treatment characteristics (e.g., change in dose, discontinuation), in the past 4 weeks, if any.
- AEs (incl. SAEs) related to or possibly related to sarecycline, observed in the past 4 weeks, as documented in the medical charts.
- Information on withdrawal from study (if occurred within the past 4 weeks).

The study Subjects will provide the following information via online survey portal or a mobile app: perceptions of current AV-related signs/severity. In case of pediatric patients, this information will be obtained from parents/caregivers as well.

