## 8.6 Safety Assessments

### 8.6.1 ***Definition of Adverse Events & Adverse Drug Reactions***

An AE is any untoward medical occurrence in a patient administered a pharmaceutical product which does not necessarily have a causal relationship with this treatment. An AE can therefore be any unfavorable and unintended sign, symptom, or disease temporally associated with the use of a medicinal product, whether or not related to the medicinal product.

The Site Investigator will use the following terms to assess the severity of each AE:

- Mild: Awareness of symptoms or signs, but easily tolerated (acceptable).
- Moderate: Enough discomfort to interfere with usual activity (disturbing).
- Severe: Interferes significantly with ability to do work or usual activity (unacceptable).

A Serious Adverse Event (SAE) is any experience that suggests a significant hazard, contraindication, side effect or precaution. With respect to human clinical experience, this includes any event which:

- results in death,
- is life-threatening,
- requires inpatient hospitalization\* or prolongation of hospitalization, unless hospitalization is for:
  - routine treatment or monitoring of the studied indication, not associated with any deterioration in condition.
  - elective or pre-planned treatment for a pre-existing condition that is unrelated to the indication under study and has not worsened since the start of study drug.
  - treatment on an emergency outpatient basis for an event not fulfilling any of the definitions of a SAE given above and not resulting in hospital admission.
  - social reasons and respite care in the absence of any deterioration in the subject's general condition.
- results in persistent or significant disability / incapacity, or

- is a congenital anomaly / birth defect,
- is a significant or important medical event that, based on appropriate medical judgment, may jeopardize the subject or may require intervention to prevent one of the other outcomes listed above.

\* Hospitalization is defined as an overnight (in-patient) stay at the hospital or emergency room.

For all AEs (either related or not related to study medication), information about the outcome (resolved or ongoing) and the action taken with the study treatment (drug withdrawn, dose reduced, dose increased, dose not changed, not applicable) will be documented.

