### **8.6.2 Documentation and Reporting of ADRs, Events with Fatal Outcome and Other Reportable Events**

The Site Investigator is responsible for assessing and documenting (in subject medical charts, as part of usual care) all AEs that occur at any time during the study. The Site Investigator will determine the relatedness, seriousness, and severity for each AE, which is then recorded in the

---

Adverse Events page of the eDCF, per study schedule of events (Appendix A). Following each subject encounter (be it, via in-person or remote encounters), the Site Investigator will evaluate the last 4-weeks of documentation (in subject medical charts) to report AEs and indicate whether those events resulted in stoppage or changes to dose of study medication.

Each AE that meets the definition of ADR will be recorded in the Adverse Events page of the eDCF and comprehensively documented on the “Adverse Drug Reaction” form to be reported within 1 working day (24 hours) of learning of the event and proactively reported to the Almirall LLC, CRO Safety Team via email or fax. ADR reporting details will be included in the Safety Reporting Plan.

For the purpose of this study, all AEs that meet the aforementioned definition of an SAE (in Section 8.6.1) that occurred during the treatment period will be reported to the sponsor as SAEs. Upon receipt of SAE data by the study CRO (collected as part of eDCF), they will be reported within 1 working day (24 hours) of learning of the event to the sponsor regardless of its relationship to the study treatment. If any additional information is needed to adequately document the SAEs, the study CRO will follow-up with the Site Investigators to ensure data completeness and will report the updated information back to the study sponsor. If an SAE results in modification of study medication dose or discontinuation of study medication and/or withdrawal of subject from the study, such information will be documented as part of eDCF and reported to the study sponsor.

As part of usual care, Site Investigator will follow Subjects concerning all SAEs and ADRs until adequate resolution or stabilization. If the SAE/ADR has not resolved or stabilized by the time the subject completed the final study visit, the Site Investigator may gather the status of the subject’s SAE/ADR within 30 days beyond the subject’s final study visit, if required.

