**Table 7.4.4.2. Overall Summary of 'Not-Related' AEs (Subject Level)**

N=300	
[P4] Subjects with at least 1 'not-related' AE	n (%)
[P4_i_4]: Intensity of adverse event, among Subjects with at least 1 'not-related' AE	n (%)
R1: Mild	n (%)
R2: Moderate	n (%)
R3: Severe	n (%)
[P4_i_3]: Action taken with Seysara, among Subjects with at least 1 'not-related' AE	
[P4_i_3r1]: Drug withdrawal / study discontinuation	n (%)
Other Actions	n (%)
[P4_i_5]: Subjects with at least 1 SAE*	n (%)
Subjects with at least 1 SAE resulting in death	n (%)

\*for not related AEs.

Note: Percentages were based on the total number of subjects in the study  
Deaths, AEs and SAEs were those that started on or after the date of the first dose of the study treatment and no more than 30 days after the date of the last dose of the study treatment.

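### Protocol 7.3, 7.4 and 7.5 word the AE item as drug-related events, which contradicts the all-AE rule in 8.6 and Appendix A and the SAP's not-related and any-type AE tables

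*Protocol*

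**What the plan says.** Protocol 7.3, 7.4 and 7.5 list what the Site Investigator completes at Weeks 4, 8 and 12. The Week 4 item reads "AEs (incl. SAEs) related to or possibly related to sarecycline, observed in the past 4 weeks, as documented in the medical charts". The Week 8 and Week 12 lists repeat the limit: "AEs (incl. SAEs) related to or possibly related to sarecycline". SAEs are expressly inside it.

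The rest of the protocol has no such limit:

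- 8.6.1 defines an AE as an event "whether or not related to the medicinal product", and requires outcome and action taken to be documented for related and unrelated AEs alike.
- 8.6.2 makes the investigator responsible for assessing and documenting "all AEs that occur at any time during the study". It continues: "The Site Investigator will determine the relatedness, seriousness, and severity for each AE, which is then recorded in the" Adverse Events page of the eDCF. SAEs go on to the sponsor "regardless of its relationship to the study treatment".
- Appendix A marks AEs/SAEs at every encounter without qualification.
- The endpoint in 3.2 is the frequency of documented AEs and SAEs, again without a causality limit.

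The SAP follows the wider scope. Table 7.4.4.2 opens with "Subjects with at least 1 'not-related' AE". Tables 7.4.4.3, 7.4.4.7, 7.4.4.8 and 7.4.4.9 are also for not-related AEs. Tables 7.4.4.1 and 7.4.4.6 report any-type events, defined as not-related AEs together with ADRs.

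**The concern.** The visit sections are a natural place for a site to look when completing an encounter. Read literally, they have the site apply its own causality judgement before entry, whereas 8.6.2 has it enter the event and record the judgement as data. If some sites did the first and some the second, the not-related counts and any-type totals would partly reflect which section a site relied on.

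Three features of the plan make such a gap hard to see or repair:

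- **Missing events look like no events.** Subject-level AE percentages use all 300 subjects as denominator, so a subject whose AE was never entered counts as event-free.
- **Detection is limited.** Protocol sections 10 and 13 describe mainly remote monitoring with occasional site visits, and the edit checks in section 11 work on incoming data. CRO queries can recover some events, but an AE that was never entered gives them little to act on.
- **The SAE route is exposed.** Under 8.6.2 the CRO forwards SAEs on receiving them through the eDCF. ADRs and fatal events have a separate form. For a non-fatal SAE judged not related, the eDCF is the only route described, so an event filtered out at entry might not reach the sponsor.

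The filter is also undefined. The causality scale in 8.6.1 has two levels, related and not related, and 'possibly related' is neither.

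**Working it through.** The plan gives no AE rate, power figure or expected count to reproduce, so the check is textual.

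**Step 1. Scope by source.**

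| Source | AE scope |
|---|---|
| Protocol 7.3, 7.4, 7.5 | Related or possibly related, SAEs included |
| Protocol 8.6.1 | Definition independent of causality; details for all AEs |
| Protocol 8.6.2 | All AEs assessed and recorded; SAEs whatever the relationship |
| Protocol Appendix A | AEs/SAEs at each encounter, no limit |
| SAP Tables 7.4.4.1, 7.4.4.6 | Not-related AEs and ADRs combined |
| SAP Tables 7.4.4.2, 7.4.4.3, 7.4.4.7 to 7.4.4.9 | Not-related AEs |

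The first row cannot be reconciled with the others as written.

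**Step 2. What each reading feeds into the tables.** The SAP maps not-related AEs to form item P4 and ADRs to P5. At event level, any-type = P4 + P5. At subject level, any-type counts subjects with P4 or P5.

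- Under 8.6.2, both P4 and P5 are filled.
- Under the literal 7.3 to 7.5 wording, only related or possibly related events are entered. That is in substance the ADR set, since 8.6.1 treats as an ADR any AE whose causal link cannot be excluded. P4 then tends to zero and the any-type figures fall towards the ADR figures.

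**Step 3. Which outputs are exposed.** The not-related tables, including their SAE rows, and the any-type totals. At subject level the any-type count loses only subjects whose AEs were all judged not related. The ADR tables (7.4.4.4, 7.4.4.5, 7.4.4.10 to 7.4.4.12) are little affected, because both readings collect those events.

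**Step 4. Size.** At event level the shortfall lies between zero (every site followed 8.6.2) and the whole P4 count (every site followed 7.3 to 7.5 literally). Narrowing that needs the AE rate, the not-related share and the proportion of sites on each reading. The documents give none of these.

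**The case against.** The strongest reply is that 7.3 to 7.5 only summarise encounter content, while 8.6.2 is the dedicated safety section. It too gives a per-encounter instruction: after each encounter the investigator reviews the last four weeks of chart documentation and reports AEs, with no relatedness filter. The form has a separate not-related item with its own onset, resolution, action, intensity and seriousness fields, so sites were presented with a place for these events. SAP 5.6.1 says in the past tense that outcome and action were documented for all AEs, related or not. The CRO also reviews data after encounters and queries sites. Finally, the study is single-arm and descriptive, safety is an additional endpoint, and the ADR counts, which say most about tolerability, are largely untouched.

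Most of this stands, and it limits the point. A reader might infer that sites were told to report related events and nothing else, or that not-related AEs were in fact lost. The documents support neither. The visit sections do not contain the word 'only', and 8.6.2, Appendix A and item P4 all point to full collection.

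The contradiction remains. The same restriction appears in all three follow-up sections, so it does not look like a single slip. A not-related field captures an event only if the site believes it is in scope. The SAP sentence repeats the 8.6.1 requirement in the past tense; it does not say which instruction sites followed when deciding what to enter.

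**Conclusion.** Protocol 7.3, 7.4 and 7.5 are wrong as written: their AE item conflicts with 8.6.1, 8.6.2, Appendix A and the SAP safety tables. The consequence is a risk of under-collecting not-related AEs and SAEs, and so of understating any-type totals, possibly unevenly across the up to 50 sites the protocol allows.

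How large the loss is, or whether there was one, cannot be determined from the documents. Any percentage would restate assumed inputs. The conclusion that ADR counts are little affected assumes that sites treat related or possibly related events as essentially the ADR set. The conclusion about the SAE route rests on the routes described in the protocol; a separate safety reporting plan is mentioned but is not among the documents.

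The correction is worth making because it costs little and protects both a named safety endpoint and SAE reporting.

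**What to change.** In Protocol 7.3, 7.4 and 7.5, replace the restricted phrase with *all AEs (incl. SAEs), each with the Investigator's relatedness assessment*, matching 8.6.2, and send sites a reminder. The cost is one phrase in three sections and one communication.

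The SAP describes conduct largely in the past tense, so collection may be over. In that case:

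1. Confirm from the eDCF wording and the site instructions which AE scope was actually collected.
2. State that scope once in SAP 6.8.
3. Only if it was restricted or mixed, footnote the any-type and not-related outputs (Tables 7.4.4.1 to 7.4.4.3 and 7.4.4.6 to 7.4.4.9) to say that not-related events may be incomplete.

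If the check shows full scope, the statement in the SAP is enough and no footnote is warranted.

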#### **7.4 Second Follow-up Encounter (Encounter # 3)**

At the completion of 8 weeks ( $\pm$  4 days) post-index date, the Site Investigators and Subjects will be asked to complete the second follow-up data collection, conducted via in-person or virtual/remote visits.

The patients will be advised to visit their site/clinician's offices to do the following:

- Drop off the second tablet/pill bottle of Seysara® (bottle # 2) supplied to them at the Wk-4 visit, be it empty or with left-over pills.
  - This may be done as curb-side interaction, without entering clinician's offices.
- Pick-up the third bottle of Seysara® supply (bottle # 3) for the next four weeks of use.
  - This may be done as curb-side interaction, without entering clinician's offices.
- Undergo AV clinical evaluation inside clinician's office, if feasible.

The Site Investigator will complete the following, based on the information documented in patient medical charts and per clinical judgment guided by observing study subject via in-person or virtual/remote visit:

- IGA of current AV severity on the face.

- Patient treatment compliance, per sarecycline pill/tablets left over in the subject-returned bottle.
- Modifications to sarecycline treatment characteristics (e.g., change in dose, discontinuation), in the past 4 weeks, if any.
- AEs (incl. SAEs) related to or possibly related to sarecycline, observed in the past 4 weeks, as documented in the medical charts.
- Information on withdrawal from study (if occurred within the past 4 weeks).

The study Subjects will provide the following information via online survey portal or a mobile app: perceptions of current AV-related signs/severity. In case of pediatric patients, this information will be obtained from parents/caregivers as well.

## 7.5 Third Follow-up & Study Close-out Encounter (Encounter # 4)

At the completion of 12 weeks ( $\pm$  4 days) post-index date, the Site Investigators and Subjects will be asked to complete the third and final follow-up data collection to close out the study. The subject encounters are expected to take place during in-person subject visits to the clinic, but remote/virtual visits will be allowed where Covid-related protocols prevent in-person visits. Subjects will be asked to drop off the third tablet/pill bottle of Seysara® (bottle # 3) supplied to them at the Wk-8 visit, be it empty or with left-over pills.

The Site Investigators will complete the following, based on the information documented in the corresponding patient medical charts and per clinical judgment guided by observing study subject via in-person or remote/virtual visit:

- Current IGA of current AV severity on the face.
- Patient treatment compliance, per sarecycline pill/tablets left over in the subject-returned bottle.
- Modifications to sarecycline treatment characteristics (e.g., change in dose, discontinuation), in the past 4 weeks, if any.

- Perceptions of sarecycline overall treatment satisfaction.
- AEs (incl. SAEs) related to or possibly related to sarecycline, observed in the past 4 weeks, as documented in the medical charts.
- Information on withdrawal from study (if occurred within the past 4 weeks).
- Newly documented changes to patient clinical characteristics, as documented in medical charts in past 12 weeks since the baseline encounter (incl. blood pressure, weight, comorbidities).
- Modifications made to concomitant medications (for AV and comorbidities) in the past 12 weeks since the baseline encounter.

In the instances when in-person subject visits take place at Week 12, for those patients for whom baseline photographic data collection was completed, corresponding Site Investigators will take photographs of patient's face to document current acne severity at Week 12.

The study Subjects will provide the following information via online survey portal or a mobile app: Perceptions of AV-related symptoms and impact of AV on emotional functioning, social functioning and activities of daily living. In a small subset of sites, clinicians will request Subjects to provide a 1–3 minute audio recording of Subject's perception of sarecycline treatment benefits experienced during the study period.

In case of pediatric patients, Caregivers will also complete a battery of questions related to their perceptions of child's current acne severity, and impact of acne on their child.

Both the Site Investigators and Subjects will be thanked for their participation in the study. No specific study close-out tasks are expected of the study Subjects. Site Investigators will be asked to submit any outstanding data queries to the research team and then close out the study records at their respective sites.

## 7.6 Early Termination Encounter (Encounter # x)

Site Investigators will attempt to follow the progress of every subject admitted to the study through to study completion. If a subject fails to complete requested study procedures (i.e., completion of online surveys), a reasonable effort will be made to contact the subject and ascertain the reason(s) for non-compliance with study procedures.

If a subject does not complete the study for any reason (including Investigator discretion), the reason and circumstances for the subject's early termination will be fully documented; if possible, the assessments specified for the forthcoming (next) study encounter will be performed.

## 8 STUDY ASSESSMENTS

PROs will be assessed with study Subjects. Sarecycline treatment effectiveness will be assessed by treating Site Investigator using IGA scores and lesion counts. Safety will be evaluated in terms of adverse events and ADRs during the treatment period.

### 8.1 PRO Assessments

A combination of a validated questionnaire and an ad hoc questionnaire prepared via modified delphi panel consensus method involving dermatologists, will be used for PRO assessments.

#### ASIS Questionnaire:

The ASIS is a 17-item questionnaire that asks patients about the signs and impact of AV (Appendix B); responses are reported as two scales: Signs (9 items), and Impact (8 items). Impact domain has two subscales, pertinent to Emotional (6 items) and Social impact (2 items). The following questions (items) correspond to each scale:

Scale	Items
Signs	1-9
Impact	10-17

All items are scored on a five-point adjectival response scale, with a potential score of 0 to 4, even though the individual item responses are different for certain question clusters. A domain score is determined by the average of scores in each scale within the domain. A total score is the average of all 17 items. Higher scores on the ASIS Sign domain, comprised of all items that assess symptoms (items 1-9), indicate the presence of more severe symptoms, whereas higher scores on the ASIS Impact domain, comprised of all of the items that assess impacts (items 10-17), indicate a greater negative impact of acne on HRQoL and appearance. The questionnaire will be administered in entirety, at baseline and at Week 12 post-index date.

At Weeks 4 & 8 post-index date, Subjects will be asked to complete ASIS Item # 9 (how is your acne on your face right now) and ASIS Item # 10 (rate how your face looked because of your acne).

Expert Panel Questionnaire:

Ten (10) ad hoc questions related to patient perception of impact of Acne on their social functioning, emotional functioning and activities of daily living were formulated based on an expert consensus involving a panel of dermatologists using modified delphi method. The items relate to how Acne impact patient's mood (anger), social interactions, general thoughts/worries about Acne and one's future goals, and impact on daily activities, including sleep (Appendix B).

All items are scored on a five-point adjectival response scale, with a potential score of 0 to 4, even though the individual item responses are different for certain question clusters. The questions will be administered in entirety, at baseline and at Week 12 post-index date.

